5.3 Assessment of Clinician and/or Subject Compliance with Study Procedural Intervention

The Project Director will regularly monitor surgical activities in-person to ensure that the surgeons are following the study procedures, performing the correct procedure, and accurately measuring and recording the incision height. Each week the Coordinating Center (CC) will compare the assignment reported on the Surgical Evaluation form against the actual assignment. The CC will issue a query for each instance where there is any disagreement between the recorded assignment and actual assignment. The CC will also compare the reported assigned height on the Surgical Evaluation against the actual height measurements. Frequency of differences greater than 0.5mm will be reported at the surgeon level on a cumulative basis. Whenever more than 5% of the actual measurements are more than 0.5 mm different than the assigned measurements, the surgeon will be reevaluated by one of the study ophthalmologists to determine what corrective measures need to be made.

6 STUDY SCHEDULE

Visit Type	Timing	Window
Eligibility Screening	Day 0	N/a (potential subjects to be screened for eligibility when they present for surgery)
Enrollment and Baseline Exam	Day 0	N/a (subjects to be enrolled right after screening)
Surgery	Day 0	0-14 days after enrollment. If surgery must be delayed more than 2 weeks, a new baseline exam should be completed.
1-day post-operative visit	Day 1	Day 1-2
Suture Removal	2 weeks after surgery	10 – 18 days after surgery
6 week follow up	6 weeks after surgery	5 to 9 weeks post-surgery
12 month follow up	12 months after surgery	11 to 18 months post-surgery
3 year follow up	3 years after surgery	30 to 42 months post-surgery

6.1 Eligibility Screening and Enrollment (Day 0)

Eligibility screening will take place at trichiasis surgery camps. Prior to this, local eye care workers will have identified all individuals with trichiasis and scheduled them for surgery. When patients present for trichiasis surgery, a trichiasis surgeon or screener will screen them for the presence of trichiasis and will note whether prior surgery has been performed on any eye that has trichiasis that day. Then the consent specialists will make a general announcement about the study and invite those who would like to learn more and possibly participate to meet individually with one of them.

The consent specialists will meet with trichiasis surgery patients in small groups to tell them about the study and then individually will assess eligibility using the Eligibility Review form. If they are eligible and interested in participating, the consent specialist will proceed to obtain informed consent with one patient at a time. The full process for

obtaining informed consent is provided in the Manual of Procedures. Those who provide consent will then meet with the project manager to be enrolled in the study.

Required Procedures/Data Collection:

- Complete Eligibility Screening form (Form 1)
- Obtain informed consent
- Collect Demographic and Tracking Information

6.2 Baseline Ocular Exam and Surgery (Day 0)

The baseline exam occurs immediately after enrollment and just prior to surgery (all happen on the same day). The goal of this exam is to characterize trichiasis severity and visual acuity prior to surgery. Baseline trichiasis severity is an important predictor of post-operative trichiasis; hence, these data will be included in all models evaluating the outcome.

After the ocular exam, the patient receives trichiasis surgery.

Required Data Collection:

- Baseline Ocular Exam Form
- Surgical Evaluation Form

6.3 Follow up Visits

Follow up visits occur 1 day, 2 weeks, 6 weeks, 12 months and 3 years following surgery. At the 2 week visit, sutures are removed. At each follow up visit the patient examiner evaluates each eyelid for the presence of trichiasis, eyelid contour abnormality and granuloma. At the one-day post-operative visit, the examiner checks the status of the surgery. If eyelashes are touching the eye or if the eyelid is completely flipped (gross over-correction) then the surgeon should adjust the surgery to correct the eyelid.

Required Procedures/Data Collection:

- Follow up visit form (2 week, 6 week, 12 month or 3 year form)
- Adverse Event Form (if applicable)

6.4 Unscheduled Visit

Between visits, the primary point of contact between subjects and the study team typically will be the community health worker (CHW) living in their community. Subjects

who experience problems between study visits will meet with the CHW who will assess the issue and determine whether a study team member should come to the village for an unscheduled study visit or whether the CHW can resolve the issue himself. If such a visit is necessary, the study team member will visit the subject and will complete an Unscheduled Visit form to document the purpose of the visit and what procedures, if any, were performed. If the CHW and study team member determine that a study visit is not required, the study team member simply needs to complete the CHW/Participant Call Log, indicating the date of the call, participant ID, reason for call and actions taken.

Required Procedures/Data Collection:

- CHW Participant Call Record
- Unscheduled Visit Form

6.5 Timeline and Feasibility of Adhering to Study Schedule

The study recruitment and follow up schedule is outlined in the table below.

Activity	Year 1 (Mar 2016 – Feb 2017)				Year 2 (Mar 2017 – Feb 2018)				Year 3 (Mar 2018 – Feb 2019)				Year 4 (Mar 2019 – Feb 2020)			
	Q1 (Mar-May)	Q2 (Jun-Aug)	Q3 (Sep-Nov)	Q4 (Dec-Feb)												
Ethics Applications	X	X	X													
Recruitment/Enrollment				Start Jan					End Mar or Apr*		Start Oct	X	End Mar			
2 and 6-week follow up				X					X	X	X	X	End May			
1 year follow up					X								Start Jan	X	Start Oct	X
Data cleaning				X	X	X			X	X	X	X	X	X	X	X
Dissemination of Study Findings (manuscripts and presentations)						X	X	X								

*Depends on when the rains start.

Activity	Year 5 (Mar 2020 – Feb 2021)				Year 6 (Mar 2021 – Feb 2022)				Year 7 (partial) (Mar 2022 – July 2022)	
	Q1 (Mar- May)	Q2 (Jun- Aug)	Q3 (Sep- Nov)	Q4 (Dec- Feb)	Q1 (Mar- May)	Q2 (Jun - Aug)	Q3 (Sep- Nov)	Q4 (Dec- Feb)	Q1 (Mar- May)	Q2 (Jun - Aug)
1 year follow up	Planned but didn't happen									
3 year follow up				X	X		X	X	X	
Data cleaning				X	X	X	X	X	X	X
Dissemination of Study Findings (manuscripts and presentations)								X	X	X

7 STUDY PROCEDURES / EVALUATIONS

Detailed methods for data collection for each of the study procedures are provided in the Manual of Procedures. This section lists the procedures and describes the general approach for data collection.

Ocular Examination: At baseline, the ocular exam will consist of an evaluation of each eyelid for the presence of trichiasis and presence of corneal opacity. At each follow up study visit, both eyelids will be assessed for the presence of trichiasis, eyelid contour abnormality and granuloma.

Visual Acuity: Visual acuity will be assessed monocularly at baseline (pre-operatively) and 12 months postoperatively using an Early Treatment of Diabetic Retinopathy (ETDRS) tumbling “E” chart on a smartphone.

Trichiasis Surgery: All participants will receive trichiasis surgery with either the BLTR or Trabut procedure outlined in the World Health Organization’s Trichiasis Surgery Manual, with exception of the incision placement for $\frac{1}{2}$ of the BLTR surgeries. In the trial, BLTR incisions will be placed 3 mm or 5 mm away from the eyelid margin, depending on randomization assignment. Detailed methods for how to measure and mark where to make the incision are provided in the Manual of Procedures.

Photographs: Photographs will be taken of each eyelid preoperatively, during surgery after incision is made, immediately postoperatively, and at each follow up visit.

8 PROVISIONS FOR MONITORING STUDY PROGRESS

Multiple levels of oversight have been built into the trial to ensure patient safety and data integrity. These include:

Internal Monitoring:

- Weekly monitoring of accumulating data to ensure complete data collection
- Weekly assessment of compliance with assignment of surgical procedure and incision height
- Regular field monitoring by local and international team members
- Active collection of adverse events during surgery and at each follow up visit.

In addition, we will follow UNC's guidelines for reporting all safety events.

External Monitoring:

- An NEI-designated Data and Safety Monitoring Board
- Annual reports to the Institutional Review Boards at each institution and to the Ethiopian ethics board (National Health Research Ethics Review Committee, Ministry of Science and Technology).

Detailed information on the managing guidelines and approaches for each of these is provided in the Manual of Procedures.

9 STATISTICAL CONSIDERATIONS

9.1 Study Hypotheses

Primary Aims:

Primary study null hypotheses:

- 1) Among BLTR surgeries, increasing the target incision height from 3 mm to 5 mm will not affect the rate of post-operative trichiasis (PTT).
- 2) BLTR surgery with a target incision height of 3 mm will have the same rate of post-operative trichiasis as Trabut surgery.
- 3) BLTR surgery with a target incision height of 5 mm will have the same rate of post-operative trichiasis as Trabut surgery.

Alternative hypotheses:

- 1) Among BLTR surgeries, increasing the target incision height from 3 mm to 5 mm will result in a 25% reduction in the rate of post-operative trichiasis (PTT).
- 2) Trabut surgery will result in a 25% reduction in the rate of post-operative trichiasis compared to BLTR surgery with a 3 mm target incision height.
- 3) Trabut surgery will result in a 25% reduction in the rate of post-operative trichiasis compared to BLTR surgery with a 5 mm target incision height.

Secondary Aims:

Null hypothesis:

- 1) Among BLTR surgeries, increasing the target incision height from 3 mm to 5 mm will not affect the rate of eyelid contour abnormalities.
- 2) Eyelids operated with Trabut will have the same rate of moderate/severe eyelid contour abnormalities rate as eyes operated with BLTR with a target incision height of 3 mm.
- 3) Eyelids operated with Trabut will have the same rate of moderate/severe eyelid contour abnormalities rate as eyes operated with BLTR with a target incision height of 5 mm.
- 4) Eyelids operated with Trabut will have the same rate of granuloma formation as eyelids operated with BLTR.

Alternative hypotheses:

- 1) Eyelids operated with the BLTR surgery and 3 mm will have fewer eyelid contour abnormalities than eyelids operated with Trabut.
- 2) Eyelids operated with Trabut will have a higher rate of moderate/severe eyelid contour abnormalities rate than eyes operated with BLTR with a target incision height of 3 mm.
- 3) Eyelids operated with Trabut will have a higher rate of moderate/severe eyelid contour abnormalities rate than eyes operated with BLTR with a target incision height of 5 mm.
- 4) Eyelids operated with Trabut will have a lower rate of granuloma formation than eyelids operated with BLTR.

9.2 Sample Size Considerations

The planned sample size for this trial is 4,953 participants. This sample size will give sufficient power to detect a 25% difference in post-operative trichiasis rates between 3 mm and 5 mm target incision heights for BLTR, a 25% difference in post-operative trichiasis rates for BLTR 3 mm versus Trabut and a difference of 25% between BLTR 5 mm and Trabut. This estimate is based on the following assumptions:

- 15% of eyelids in the BLTR 3 mm target height group will develop post-operative trichiasis during the 12 months following surgery
- Two-sided alpha error = 5%
- Power = 80%
- 40% of participants will have 2 eligible eyes
- The correlation between 2 eyes of an individual is 0.24
- 5% loss to follow up.

Based on these assumptions, the table below shows the total number of participants needed within the 3 arms combined.

Prevalence in control group	RR	Subjects per Arm	Total number of subjects In the 3 arms if 100% bilateral	Total number of surgeries needed	Only 40 % of surgeries will be bilateral # of surgeries	Additional Subjects (surgeries) to accrue the total number needed	Total number of subjects to be enrolled	Increase to account for 5% lost to follow-up
15%	0.70	743	2229	4458	3121	955 (1337)	3184	3351

16%	0.70	690	2070	4140	2898	887 (1242)	2957	3112
15%	0.75	1098	3294	6588	4612	1411 (1976)	4705	4953
16%	0.75	1019	3057	6114	4280	1310 (1834)	4367	4597

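### Section 9.2: the listed assumptions give about 3,550–3,560 participants (about 3,705 with continuity correction), not 4,953, and the 5 mm versus Trabut power claim has no stated 5 mm rate

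*Combined protocol and SAP*

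**What the plan says.** Section 9.2 sets the total: "The planned sample size for this trial is 4,953 participants". It claims power for a 25% relative difference in each of three pairwise comparisons, the third being "a difference of 25% between BLTR 5 mm and Trabut". The listed assumptions include "15% of eyelids in the BLTR 3 mm target height group will develop post-operative trichiasis during the 12 months following surgery", "Two-sided alpha error = 5"%, 80% power, 40% of participants with two eligible eyes, "The correlation between 2 eyes of an individual is 0.24" and 5% loss. The table is then introduced with "Based on these assumptions, the table below shows the total number of participants needed within the 3 arms combined". Its 15%, RR 0.75 row starts at 1,098 subjects per arm as if everyone were bilateral and ends at 4,953. The rate column is headed "Prevalence in control group" and names no arm.

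Section 9.1 gives three alternatives. The first is that "increasing the target incision height from 3 mm to 5 mm will result in a 25% reduction in the rate of post-operative trichiasis". The second puts Trabut 25% below 3 mm, and the third puts Trabut 25% below 5 mm. Section 9.3 plans all three comparisons. Neither 9.2 nor 9.3 says whether the 5% applies to each one.

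**The concern.** The listed inputs define a standard two-proportion calculation with a design effect, so the 1,098 should be recoverable to within rounding or the choice of formula. It is about 39% too large. At least one input must be misreported or missing from the list, and a reader cannot tell what alpha or power the trial was built for.

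The third comparison has a separate gap. It serves a primary objective, but 9.2 gives a rate only for the 3 mm arm. Power for a fixed relative reduction depends strongly on the base rate, so this claim cannot be checked from the section that makes it.

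**Working it through.** **Inputs (section 9.2).** p1 = 0.15; RR 0.75, so p2 = 0.1125; two-sided alpha 0.05 (z = 1.960); power 80% (z = 0.842); correlation 0.24; 1.4 eyes per participant; 5% loss; three equal arms.

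**The plan's later steps reproduce.** 1,098 × 3 = 3,294 subjects; × 2 = 6,588 surgeries; / 1.4 = 4,705; / 0.95 = 4,953. In short, enrolment = n × 6 / 1.4 / 0.95.

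**The starting figure does not.** Independent eyes per arm, with p̄ = 0.13125:

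- Pooled: [1.960·√(2·p̄(1−p̄)) + 0.842·√(p1(1−p1) + p2(1−p2))]² / (p1−p2)² = [1.960 × 0.4775 + 0.842 × 0.4768]² / 0.0375² = 1,272.
- Unpooled: (1.960 + 0.842)² × [p1(1−p1) + p2(1−p2)] / (p1−p2)² = 1,269.
- Pooled with continuity correction: (n/4)·[1 + √(1 + 4/(n·0.0375))]² = 1,324.

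All-bilateral subjects per arm = eyes × 1.24 / 2, which is 789, 787 and 821. By the table's later steps: 787 → 3,550; 789 → 3,559; 821 → 3,704.

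**All four rows show the same excess** (subjects per arm):

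| Control rate, RR | Table | Pooled | Ratio | With continuity correction | Ratio |
|---|---|---|---|---|---|
| 15%, 0.70 | 743 | 533.9 | 1.392 | 561.1 | 1.324 |
| 16%, 0.70 | 690 | 495.6 | 1.392 | 521.1 | 1.324 |
| 15%, 0.75 | 1,098 | 788.4 | 1.393 | 821.2 | 1.337 |
| 16%, 0.75 | 1,019 | 731.6 | 1.393 | 762.3 | 1.337 |

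The unpooled ratios are 1.396–1.397. This is not a slip in one row.

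**Several different input sets fit** (rows in the same order; table 743, 690, 1,098, 1,019):

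| Inputs | Result |
|---|---|
| 5%, 90% power, correlation 0.24, continuity correction | 742, 689, 1,088, 1,010 |
| 5%/3, 80% power, correlation 0.24, continuity correction | 740, 687, 1,085, 1,007 |
| 5%, 90% power, correlation 0.29, pooled | 743.3, 689.9, 1,097.7, 1,018.6 |
| Listed inputs (pooled) × 1.392 | 743.2, 689.9, 1,097.5, 1,018.5 |

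Each departs from the list in 9.2. The table does not identify which was used.

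**The 5 mm rate.** Alternative 1 with 15% gives 5 mm = 0.75 × 15% = 11.25%. Alternative 2 gives Trabut = 11.25%. The ratio of Trabut to 5 mm is then 1.00, not the 0.75 of alternative 3. Alternatives 2 and 3 together give 5 mm = 11.25% / 0.75 = 15%. Section 9.1 therefore yields two different rates.

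**Power with 4,705 retained.** Eyes per arm = 4,705 / 3 × 1.4 = 2,196. With the table's design effect the effective number is 2,196 / 1.24 = 1,771. RR 0.75, no continuity correction:

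| Rate in comparator arm | 5% unsplit | 5% split three ways |
|---|---|---|
| 10% | 75% | 59% |
| 11.25% | 80% | 66% |
| 13% | 86% | 74% |
| 15% | 91% | 82% |

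The 15% row covers both comparisons against 3 mm. For 5 mm versus Trabut, every row is an assumed 5 mm rate. Allowing for the actual mix of one-eye and two-eye participants gives 1,931–1,953 effective eyes per arm and, at 15%, power of 93% unsplit and 86% split.

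**The case against.** The strongest reply is that 3,550–3,560 covers only the comparisons against 3 mm, and that the third comparison justifies the larger number. Taking 5 mm at 11.25% from alternative 1 and Trabut 25% lower at 8.44%, the listed alpha, power and correlation need 4,915 (unpooled) to 4,923 (pooled), within 1% of 4,953. The arithmetic is right, and power for that comparison at an unsplit 5% is then about 80%. It does not rescue the section. The same reading misses the table's two RR 0.70 rows by 7–8%, the table gives 15% and 16% as its control rates, and alternatives 2 and 3 imply 15% for 5 mm instead. It is fair to say that alternatives for three separate tests need not all be true at once, but that is why the third test needs its own stated rate.

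Three further points stand as limits on the concern. The documents mention no alpha split, and 5% per test is the plain reading, so the split figures are conditional. The all-bilateral design effect is the table's choice; using the 40% bilateral share directly (1.592 / 1.4 = 1.137) gives about 3,263, which is further from 4,953. And the discrepancy runs in the safe direction for the 3 mm comparisons.

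**Conclusion.** The concern holds. A total said to follow from the listed assumptions exceeds what they give by about 39% (about 34% with continuity correction), consistently across the table, and the cause cannot be settled from the documents. At the stated 5% per comparison, the two 3 mm comparisons are not underpowered: about 91% by the table's design effect, not 80%. For 5 mm versus Trabut, whether 4,953 suffices depends on a rate the plan does not give. At an unsplit 5% it reaches 80% power if the 5 mm rate is about 11.25% or higher, and falls to 75% at 10%. These figures assume RR 0.75, 40% bilateral, correlation 0.24 and 5% loss as listed; the 10–15% range for 5 mm is an assumption made here.

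**What to change.** Keep N and correct section 9.2. State the alpha for each comparison, the power, the correlation, the formula (including any continuity correction) and any further factor that produced 1,098. State the assumed rate in each arm for each of the three comparisons, and say which arm the table's control rate refers to. Then replace the single 80% with the power that 4,953 delivers for each comparison under those inputs. The power table above can serve as a guide until the actual inputs are confirmed. The cost is text only; enrolment does not change.

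### The sample-size step from 100% to 40% bilateral keeps the number of surgeries fixed, so the clustering allowance no longer fits the eye mix: a 9.0-10.3% excess if Subjects per Arm includes the factor 1.24, a shortfall if it includes none

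*Combined protocol and SAP*

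**What the plan says.** Section 9.2 (Sample Size Considerations) states: "The planned sample size for this trial is 4,953 participants". Its assumptions are a 15% event rate in the BLTR 3 mm arm, a 25% relative difference, two-sided alpha of 5% and 80% power. They also include "40% of participants will have 2 eligible eyes", "The correlation between 2 eyes of an individual is 0.24" and "5% loss to follow up".

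The table is presented as resting on these assumptions. It begins with Subjects per Arm (1,098 in the 15%, RR 0.75 row) and multiplies by three for an all-bilateral trial (3,294). Doubling gives 6,588 surgeries. The next column, headed "Only 40 % of surgeries will be bilateral # of surgeries", shows that 3,294 subjects would supply only 4,612 surgeries at the expected share. The table then adds 1,411 subjects (1,976 surgeries) to return to 6,588, and inflates for loss. The heading speaks of 40% of surgeries and the assumption of 40% of participants; the arithmetic uses participants.

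Section 4.4.1 randomises by participant, with both eyes in the same arm. Section 9.3 analyses eyes with generalized estimating equations (GEE) and names no working correlation.

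**The concern.** Both eyes of a participant share an arm, so a correlation of 0.24 makes a pair of eyes worth less than two independent eyes. A participant with one eye carries no such penalty. An eye count worked out for an all-paired trial is therefore not the count needed when 60% of participants contribute one eye. The table holds the count constant in all four rows, and no column after Subjects per Arm uses the correlation.

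At stake is whether the enrolment target and the claimed 80% power agree with the plan's own correlation and bilateral share. The issue is separate from whether 1,098 is right. Replacing it with another all-bilateral figure that includes the 1.24, and leaving the later columns alone, would carry the same proportional excess into the new total.

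**Working it through.** **Inputs (section 9.2).** Correlation 0.24; 40% of participants bilateral, so 1.4 eyes per participant; 5% loss; three arms; 1,098 subjects per arm if all bilateral.

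**1. The plan's own figure.** 3 x 1,098 x 2 = 6,588 surgeries; 6,588/1.4 = 4,705; /0.95 = 4,953. This reproduces. The same chain gives the other three totals (3,351, 3,112 and 4,597) to within one participant.

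**2. Design effects.** All eyes paired: 1 + 0.24 = 1.24. At 40% bilateral, the share of eyes that are paired is 0.8/1.4 = 57%.
- Independence working correlation: design effect 1 + 0.24 x 0.8/1.4 = 1.137.
- Exchangeable working correlation: information per participant 0.6 + 0.8/1.24 = 1.245 independent eyes.

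**3. If Subjects per Arm contains 1.24.** Independent eyes needed = 6,588/1.24 = 5,313.
- Independence: 5,313 x 1.137/1.4 = 4,315; /0.95 = 4,543.
- Exchangeable: 5,313/1.245 = 4,267; /0.95 = 4,491.

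The ratio of planned to needed is 1.24/1.137 = 1.090 or 1.24 x 1.245/1.4 = 1.103. It is the same in every row: 3,351 becomes 3,074 or 3,039; 3,112 becomes 2,855 or 2,822; 4,597 becomes 4,216 or 4,168.

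Power at 4,953, taking 1,098 as the 80% point: Phi(2.802 x sqrt(1.090) - 1.960) = 83.3%; with 1.103, 83.7%.

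**4. If Subjects per Arm contains no design effect.** The 6,588 are then independent eyes.
- Independence: 6,588 x 1.137/1.4 = 5,351; /0.95 = 5,633.
- Exchangeable: 6,588/1.245 = 5,291; /0.95 = 5,569.

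| Content of Subjects per Arm | Need, independence | Need, exchangeable | 4,953 against need |
|---|---|---|---|
| Includes 1.24 | 4,543 | 4,491 | 9.0% or 10.3% above |
| No design effect | 5,633 | 5,569 | 12.1% or 11.1% below |

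**5. Does 1,098 follow from the stated inputs?** For 15% against 11.25%, two-sided 5% alpha and 80% power, the usual two-proportion formula gives 1,272 eyes per arm. Then 1,272 x 1.24/2 = 789 subjects (821 with continuity correction), not 1,098. The other rows give 534, 496 and 732 against 743, 690 and 1,019.

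From the stated inputs throughout, 3 x 1,272 x 1.137/1.4/0.95 = 3,262 (independence), or 3 x 1,272/1.245/0.95 = about 3,225 (exchangeable). On those inputs 4,953 is 52-54% above the need, and its power is about Phi(2.802 x sqrt(1.52) - 1.960) = 93%.

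**The case against.** The strongest objection is that the table never shows the factor 1.24 inside Subjects per Arm. That stands. The documents give no formula for the column, and with the stated alpha and power the factor does not produce 1,098. Back-fitting does not settle the matter. Alpha of 0.05/3 with 90% power and no design effect gives 1,094 and matches all four rows within 0.4%. Alpha of 0.10 with 95% power, a log odds ratio formula and the 1.24 gives 1,095 and matches about as well. Both need an alpha and a power that the plan does not state. What favours the 1.24 is that the correlation is a listed assumption, no later column uses it, and the three-arm total is headed as all-bilateral.

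A reader might therefore infer that every total is too high by 9-10% whatever lies behind Subjects per Arm, or that some 410-460 people are surplus. The documents do not support either inference. The ratio does not depend on the size of that column, but it does depend on its content, and with no design effect the sign changes. Nor is 9-10% the full discrepancy in the totals, because 1,098 itself is unexplained.

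It can also be said that sizing for all-paired eyes is a cautious simplification and that GEE will handle the actual mix. Both are fair. On the natural reading the error is conservative, and the validity of the analysis is not affected. The stated power still does not belong to the stated enrolment.

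**Conclusion.** The point holds conditionally. Holding surgeries fixed while the bilateral share falls from 100% to 40% does not agree with the plan's own correlation, whether Subjects per Arm contains the all-bilateral factor or no design effect.

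On the reading that the assumptions imply (1.24 included), this step alone overstates the need by 9.0-10.3% in each row; the power of 83-84% at 4,953 further assumes that 1,098 is the 80% point. On the other reading, the correlation is used nowhere and 4,953 is about 11-12% too low. The step would be right, under independence weighting, only if the column already carried the mixed value 1.137, which conflicts with the all-bilateral heading of the three-arm total.

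These figures assume a correlation of 0.24, 40% of participants bilateral, and the same 5% loss in one-eye and two-eye participants. They isolate the conversion step. They do not show that the trial as a whole is over- or under-sized, which cannot be judged until the origin of 1,098 is stated.

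**What to change.** In section 9.2:

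- State the formula, alpha, power and design effect behind Subjects per Arm.
- Replace the fixed-surgeries columns. Start from the number of independent eyes required, multiply by 1 + 0.24 x 0.8/1.4 = 1.137, then divide by 1.4 eyes per participant and by 0.95. If an exchangeable working correlation is intended, say so and use 1.245 independent eyes per participant instead.
- Restate the four totals, or keep 4,953 and restate the power it delivers.
- Reword the column heading so that 40% refers to participants, as in the assumption.

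The cost is one recalculated table and a sentence or two of text. It requires no change in enrolment or conduct.
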